This document describes the statistical analysis plan (SAP) for the PROVID-LD trial. The SAP was developed according to guidelines found in ICH E91. This SAP contains more technical and detailed elaboration of principal features of the analysis describes in the protocol, and includes procedures for executing the statistical analysis of the primary and secondary variables. Planned ancillary studies will not be included in this SAP and will have their own separate SAP. Others unplanned exploratory analyses not identified in the SAP will be clearly identified in the reporting as well as any deviation in the analyses from this original SAP.

The SAP should be executed once the trial database lock (DBL) has been achieved. Analyses will be double-blinded for the randomization group. All the analyses will follow the Statistical Analysis Plan (SAP) described in this document. Analyses will be done under the responsibility of the trial statistician at the Data Coordinating Center (Applied Clinical Research Unit (URCA), CHU-Sainte-Justine, Montreal).

During the analysis processes, the study Principal Investigator, the Executive Committee and the Steering Committee will be kept blind to the randomization group until final disclosure of the study results.

5. Statistical analysis plan revisions

Any changes to the SAP will be logged in the following table:

Protocol version	Updated	SAP	Section number	Description	of	Date changed
	version			and reason	for	
				change		

6. Roles and responsibilities

Chercheurs

Université de Sherbrooke

[name], PhD, principal investigator [name], immunologie et biologie cellulaire, co-investigator [name] [name], statistiques, co-researcher [name], MSc, santé publique, co-researcher [name], biologie, co-researcher [name], PhD, gériatrie, co-researcher [name], statistiques, co-researcher [name], MSc, infectiologie, co-researcher [name], microbiologie, collaborator [name], MSc, cardiologie, collaborator [name], MSc, pneumologie, collaborator [name], immunologie et infections bactériennes, collaborator [name], médecine, collaborator [name], radiologue, collaborator

[name], méthodologie, co-investigator [name], PhD, infectiologie, collaborator [name], nutrition, collaborator

CHU Ste-Justine

[name], Biostatistics, Lead Biostatiscian, co-researcher [name], Statistician [name], Statistician

Partenaires collaborateurs

Lallemand Solutions Santé [name] [name] Coordination Centre de recherche du CHUS [name]. [name], Data manager

Authorized and approved by Trial steering and management committeeNameSignatureDate

Section 2: Introduction

7. Background and rationale

Probiotics may be considered as an option of treatment for long COVID since they have anti-viral effect, trigger immunomodulation and have low side-effects. This randomized controlled trial aims to reduce the number of patients with long COVID by 25% 90 days after the COVID-19 diagnosis by taking probiotics in a symptomatic population, self-caring at home. During the acute phase of the disease, participants will take two capsules (probiotics or placebo) per day for 10 days and one capsule (probiotics or placebo) per day for the following 15 days. A follow-up will be done twice during the acute phase, 14 days and 28 days after starting to take the investigational product (compliance to treatment, side effects, etc.). At inclusion and at Day14, Day30 and Day90 after the COVID-19 diagnosis, a questionnaire will be administered (COVID-19 symptoms, anxiety, functioning difficulties, etc.) and 2 saliva (microbiota analyzes) self-samples will be performed.

COVID-19 disease caused by a new coronavirus (SARS-CoV-2) has received worldwide attention. No effective treatment against COVID-19 is available and the current vaccination appears essential to control the pandemic. However, many questions remain, such as the durability of immunity and the appearance of variants. While the acute phase has been widely studied, the long-term consequences are unknown, and a new burden is emerging: the long COVID. The long COVID is defined by the persistence of symptoms of the disease for more than 4 weeks after diagnosis. Several strong arguments support the study of probiotics for COVID-19: 1) probiotics act on viruses by various well described mechanisms (reduction of absorption, cellular internalization of the virus, production of metabolites/substances having a direct antiviral effect and immunomodulation); 2) probiotics are considered with a high level of evidence (meta-analysis) to reduce diarrhea (associated with antibiotics and Clostridium difficile) and for respiratory tract infections and 3) probiotics are affordable and available with low side-effects.

8. Study Objectives

Primary objective: Reduce by 25% the number of patients with LONG-COV during follow-up at D90 by taking probiotics during the acute phase of COVID-19.

Secondary objectives (Obj S):

Objective S1: Compare the proportion of patients presenting COVID-19 symptoms and severity of symptoms at D14, D30 and D90 by taking probiotics during the acute phase of COVID-19.

Objective S2: Describe the symptoms severity and evolution by study group and baseline characteristics.

Objective S3: Determine/identify prognostic factors measured at baseline (inclusion) associated with LONG-COV (sociodemographic, clinical factors).

Section 3: Trial Methods

9. Trial design

Inclusion Criteria:

- 18 years and over
- ≤ 10 days between the COVID-19 diagnosis and the inclusion
- Having symptoms of the COVID-19 at inclusion
- Living in Quebec for the next 90 days
- Self-caring at home
- Able to take medication alone
- With access to a phone or to the Internet
- Able to give informed consent

Exclusion Criteria:

- Taking probiotic supplements at inclusion
- Taking antibiotics for a reason other than COVID-19 at inclusion
- Allergies to soy, lactose, yeast, maltodextrin, vitamin C, potato starch, magnesium stearate, hypromellose or titanium dioxide
- Has a chronically weakened immune system (AIDS, lymphoma, chemo-radiocorticosteroid therapy, immunosuppressive pathology)
- Has any immunosuppressive medication (Anti-rejection treatment following an organ transplant)
- Was treated with chemo-radio-corticosteroid therapy in the last 6 months
- Has active cancer
- Already taking part in another randomized clinical trial
- Pregnant or planning to become pregnant; breastfeeding or will be breastfeeding in the next few months

10. Randomization

Randomization with a 1:1 ratio, probiotics vs. placebo, in the first line immediately after inclusion. Prior to the start of the study, the randomization list will be generated by the statistician considering age and gender stratification. Age stratification will be done in 4 strata: 18-29 years; 30-49 years; 50-69 years and 70 years and older.

Randomization will be done via the REDCap application. The statistician will create different randomization tables according to gender (female/male) and age strata. These tables will then be imported into REDCap for automatic randomization based on the age and sex information of each participant.

During the course of the trial and until the database is locked, study personnel at the site (principal investigator and research team) and at the Sponsor (research specialists and laboratory manager) will not be informed of the group allocation. Based on a blinded randomization method (according to the algorithm built into the REDCap platform), participants will be assigned to one of the 2 groups. The CHUS pharmacy will prepare the products according to the allocation on REDCap. Lallemand Health Solutions will deliver all products before the beginning of the study to the CRCHUS pharmacy.

11. Level of statistical significance

Because LONG-COV is a new disease, few data are available to determine the proportion of patients with persistent symptoms or the occurrence of symptoms associated with LONG-COV at D30 or D90. To be conservative in the size calculation, we used an expected proportion of 50% in the placebo group at D90. Because the procedure is over-the-counter and inexpensive, we calculated the size to detect a moderate relative difference of 25% (50% versus 37.5%) with a two-sided alpha of 5% and power of 80%. 494 patients (247 per group) are required. Considering a 20% attrition at D90, a total of 618 patients will have to be recruited.

Final analyses will begin in September of 2023 after database lock.

Unless otherwise specified, the alpha will be set at 0.05 for statistical significance.

12. Adverse events reporting

All effects experienced by participants for the duration of the study (from randomization to 30 days after the last dose) must be documented (noting duration, intensity, severity, predictability, causality). All unexpected events (not listed above) that are potentially related to intervention and considered serious must be reported within 24 hours: to the ethics committee, to Health Canada and to Lallemand Health Solutions. A full report should be sent within 7-15 days, depending on the seriousness of the situation.

13. Definition of adherence and how adherence will be presented

Adherence will be estimated via self-reported adherence in the logbooks at D14 and D28 completed online or on paper (according to the preference of the participant). If at least 80% of the doses prescribed was taken i.e. 20 pills out of 25, we consider that the participant adhered to the protocol.

14. Lost to follow-ups

We initially anticipated that 20% of participants will be lost to follow-up, according to the 1st PROVID-19 pilot study statistics. Indeed, 21.4% were lost to follow-up prior to 90 days.

15. Definition of analysis populations e.g. Intention-to-treat, per-protocol

Intent to treat analyses will include all participant randomized to either control or intervention arm including participants lost to follow up.

Per-protocol analyses will include all participant randomized to either control or intervention arm, excluding participants lost to follow up or those with less than 80% adherence to the assigned intervention.

16. CONSORT diagram

Per recommendations in the CONSORT guidelines, the statistician will generate a flow chart indicating the number of individuals screened and enrolled, the reasons for ineligibility, the number of individuals randomized, and the number of individuals in each arm with data at each time point. Some participants have incomplete forms mid-study but were not lost to follow-up, hence the differences in Totals.

At D30

At D90

Total %

Total

251

239

239

76.8

11

13

72

23.2

12

12

67

21.8

Intervention

n = (307)

Completed

(at least

partially)

307

261

251

240

240

78.2

At Baseline

At D14

At D30

At D90

Total %

Total

Statistical Analysis

17. Descriptive analyses and positivity checks

Distribution of sociodemographic and clinical variables measured at inclusion will be described for each group. The proportion of missing data will be described for each variable.

The probability of intervention conditional on baseline variables will be calculated for all observations to confirm the effectiveness of randomization and to verify the balance of baseline factors in each intervention arm. Overall probability will be graphed to confirm that there are no violations of positivity. Should there be positivity violations, the statistician will investigate and characterize participants who have a less than 5% or greater than 95% probability of intervention. The statistician will then notify the investigators and discuss whether a restriction of the analysis is necessary. Potential covariates associated with the outcome will be evaluated and considered in the analysis to limit the confusion bias.

To assess the quality of participant blinding, participants assessment of their arm will be compared against the true randomization status.

A table describing the demographic and clinical characteristics at baseline randomization will be generated, however statistical testing will not be done comparing individual variables between groups.

Participation in follow-up assessments and completeness of outcome data will be calculated and compared for each time point by study arm. A sensitivity analysis on loss to follow-ups will be performed using weights or extreme case scenarios. In the latter method, we will assume that all losses to follow-up had or did not have LONG-COV at D90, enabling us to estimate the potential bias.

18. Intention to treat

For the primary analyses, we will follow an intention to treat model. All participants will be assigned intervention status based on their randomized assignment. We will use an inverse probability of censoring for missing outcome data. Participants lost to follow-up will be censored.

19. Adherence per protocol analysis

Per-protocol analyses will include all participant randomized to either control or intervention arm, excluding participants lost to follow up or those non-adherent to the assigned intervention. Adherence will be estimated via self-reported adherence in the logbooks at D14 and D28 completed online or on paper (according to the preference of the participant). If at least 80% of the doses prescribed was taken i.e. 20 pills out of 25, we consider that the participant adhered to the protocol.

20. Long-term COVID-19 (LONG-COV)- Outcome definition

Background

Based on the WHO, long-term COVID is defined as follows: "It is defined as the continuation or development of new symptoms 3 months after the initial SARS-CoV-2 infection, with these symptoms lasting for at least 2 months with no other explanation. »

(https://www.who.int/europe/news-room/fact-sheets/item/post-covid-19-condition)

Definition of COVID-LD in PROVID-LD

Long-term COVID-19 (LONG-COV) status was defined according to three criteria:

A Binome of COVID-19 symptoms from FLU-PRO:

A binome is a recurrent symptom, i.e. present at D30 and D90. We selected participants with at least one symptom recorded at D30 and D90 with a value of moderate level or more ([2:4]). Also, we selected the participants who presented the symptoms of "Loss of Taste" and/or "Loss of Smell" at D30 or D90.

A Binome of symptoms from the Quality of life indicators:

We reviewed the participants who showed a moderate level or more ([2:3]) at D30 and D90 for difficulty performing current activities, pain/comfort and anxiety/depression. Worsening of Functioning difficulties:

For the functioning difficulties, participants were asked to estimate their functional status before COVID-19 in the form at D30 and in the form at D90. The smaller value was retained if an inconsistency was detected between these two values. We harmonized the recorded values pre-COVID-19 at D30 and D90. We selected participants with a non-zero value at D30 and a difficulty value at D90 higher than pre-COVID-19 for Concentration and memory, and the ability to Take

care of themselves.

The status of FLU-PRO and quality of life indicators before COVID-19 disease was initially unknown. Thus, we have operationalized the WHO's definition to select patients. If at least one of the criteria was met, the participant would be qualified for an expert's review. Every diagnosis based on Binomes was reviewed by expert on LONG-COV physicians. Those initially selected who potentially qualified for LONG-COV were called after the study to verify if symptoms were present or not before the positive detection of COVID-19. The final decision was on the expert physician responsibility.

First, initial analyses were carried out using a binary LONG-COV criterion (yes/no). Secondly, LONG-COV cases were categorized according to their level of severity and symptoms profile over time. Participants in the intervention and the placebo arms of the trial were compared.

21. Descriptive analyses of outcome measures

Distribution of score measures will be calculated for each of: COVID-19 symptoms (FLU-PRO and loss of smell and/or taste), quality of life indicators (GAD-7) and functioning difficulties (WG-SS) at D30 and D90 timepoints. The distributions will be generated overall and comparatively by intervention arm using t-test or rank sum testing as appropriate based on the distributions.

Individual symptom frequency for those items included and not included in the FLU-PRO instrument score will be described and compared between groups using chi-squared or fishers exact tests as appropriate.

22. Stratifying variables

The analysis will follow the randomization strategy. Gender and age were used as stratifying variables. We will use the same categories in the analysis.

23. Primary outcome analyses

The proportions of participants with LONG-COV at D90 will be compared using the Cochran-Mantel-Haenszel test, adjusting for stratification.

24. Secondary outcome analysis

S1: The presence and severity of symptoms at D14, D30 and D90 will be explored by doing a descriptive analysis for each study-time. The proportions of participants with LONG-COV at D14, D30 and D90 will be compared using the Cochran-Mantel-Haenszel test, adjusting for stratification. A table will summarize the proportion of each symptoms at each time with the means severity per study arm.

S2: A GEE analysis (with linear or logit link function depending on the variables) will use Symptoms Severity as the outcome over all time points and include baseline characteristics. This is to assess whether the intervention reduces the number and severity of symptoms. A faster decrease is expected with intervention.

We will supplement these analyses with a GEE (with a logit link function), using a binary LONG-COV status as the outcome and including measurements at Baseline, D14, D30 and D90 and indicator variables for stratification.

If there are differences in censoring by group, an additional GEE model will be used with inverse probability of censoring weights (IPCW) to assess the bias potentially induced by attrition during follow-up to D90. This method first estimates the probability of dropout to construct IPCWs, and then fits the GEE model with these IPCWs.

S3: Finally, logistic regression will be used to determine potential prognostic factors at baseline associated with LONG-COV at D90. The relationship between other variables including self-reported health, and LONG-COV will be assessed.

25. Adverse and Serious adverse events

Adverse events (AE), including serious adverse events (SAE), will be monitored and tracked using a logbook. They will be coded according to MedRA standards and will be summarized per intervention group.

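### The pill count in the adherence rule (20 of 25) does not match the SAP's own regimen, which totals 35 capsules

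*SAP*

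**What the plan says.** Section 7 describes the intake in both arms as "two capsules (probiotics or placebo) per day for 10 days and one capsule (probiotics or placebo) per day for the following 15 days". No other section of the SAP gives a regimen.

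Section 13 says how adherence is measured, "Adherence will be estimated via self-reported adherence in the logbooks at D14 and D28", and then sets the threshold: "If at least 80% of the doses prescribed was taken i.e. 20 pills out of 25". Section 19 repeats this rule with the same pill count.

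Section 15 uses the threshold to define the per-protocol population, "excluding participants lost to follow up or those with less than 80% adherence to the assigned intervention". Section 18 keeps the main analysis apart from it: "For the primary analyses, we will follow an intention to treat model".

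**The concern.** The adherence sentence contains a percentage and a count that are presented as the same thing. Under the Section 7 regimen they are not: the percentage gives a cut of 28 capsules, the count a cut of 20. The two figures agree only if the denominator is 25, and no 25-pill regimen appears in the SAP.

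Together with loss to follow-up, this rule is the whole definition of the per-protocol set. A SAP should fix such a rule so that two programmers working from the same logbooks arrive at the same set. Here one could use 20 capsules, another 28 capsules and a third 20 dosing days, each with some support in the text. The reported adherence rate would differ in the same way.

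**Working it through.** **Inputs.** Regimen: 2 capsules/day × 10 days, then 1 capsule/day × 15 days (Section 7). Threshold: 80%, worked as 20 of 25 pills (Sections 13 and 19).

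**The plan's own figure.** 20/25 = 0.80. The percentage is right for a denominator of 25, and Sections 13, 15 and 19 all use 80%. The question is where 25 comes from.

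**Denominator from Section 7.**
- Capsules: 2 × 10 + 1 × 15 = 35
- Dosing days: 10 + 15 = 25

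So 25 is reproduced as days and not as pills.

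**The stated count against 35 capsules.**
- 20/35 = 57.1%
- 0.80 × 35 = 28 capsules, which is 28 − 20 = 8 more than the stated count
- Totals from 20 to 27 capsules (20/35 = 57.1% to 27/35 = 77.1%) pass the count and fail the percentage
- Full intake scored on a denominator of 25 pills: 35/25 = 140%

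**Whether reading 25 as days settles it.** Twenty complete days means five missed days:
- all five missed are two-capsule days: 35 − 10 = 25 capsules, 25/35 = 71.4%
- all five missed are one-capsule days: 35 − 5 = 30 capsules, 30/35 = 85.7%

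A days rule is therefore not the same as an 80%-of-capsules rule.

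**Intake patterns under the three readings** (a day counts only if all its capsules were taken):

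| Pattern | Capsules | Complete days | 20 pills | 28 capsules | 20 days |
|---|---|---|---|---|---|
| Everything to day 10, then stopped | 20 (57.1%) | 10 (40%) | pass | fail | fail |
| Everything to day 18, then stopped | 28 (80%) | 18 (72%) | pass | pass | fail |
| Everything to day 19, then stopped | 29 (82.9%) | 19 (76%) | pass | pass | fail |
| Five two-capsule days missed, nothing else | 25 (71.4%) | 20 (80%) | pass | fail | pass |
| One capsule on each of the 25 days | 25 (71.4%) | 15 (60%) | pass | fail | fail |

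In the last row, if any intake counts as a day taken, the score is 25/25 and the days rule is passed. A days rule thus also needs a definition of a complete two-capsule day.

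**Overlap of the days and capsule rules.** Let a = complete two-capsule days (0 to 10) and b = one-capsule days taken (0 to 15), giving 11 × 16 = 176 combinations.
- Days rule, a + b ≥ 20: 21 pass
- Capsule rule, 2a + b ≥ 28: 20 pass
- Both: 17. At least one: 21 + 20 − 17 = 24
- Days only, 21 − 17 = 4: (a, b) = (5,15), (6,14), (6,15), (7,13), which is 25 to 27 capsules
- Capsules only, 20 − 17 = 3: (9,10), (10,8), (10,9), which is 18 or 19 days

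Seven of the 24 combinations are classified differently. These are unweighted patterns of complete days. They show that the rules diverge near the threshold and are not an estimate of how many participants would be reclassified.

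**The case against.** The best defence is that the rule is framed in terms of doses. If a dose is one day's intake, Section 7 gives exactly 25 doses, 20 of them is exactly 80%, and the only slip is the word pills. This is a plausible origin of the figure. It does not settle the rule, because no section defines a dose as a day, the word pills stands in both Sections 13 and 19, and a days rule selects a different set from a capsule rule.

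A second objection is that Section 7 is a background summary and the protocol is not at hand, so Section 7 could be the text that is wrong. That is fair. The figure of 28 of 35 holds only under the Section 7 regimen, and this review takes no position on which passage is correct. The contradiction within the SAP remains either way.

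Third, the logbook or the protocol may already say what is recorded and what makes a two-capsule day complete. That may be so, but neither can make 20 of 25 pills agree with a 35-capsule regimen.

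Finally, the consequence is limited, since the primary analysis is by intention to treat. This stands and bounds the importance of the point. It is also fair that Section 15 has no separate defect: it relies on the adherence definition elsewhere and only inherits its ambiguity.

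**Conclusion.** The point holds. Under the SAP's only stated regimen, the worked pill count is 57.1% of the prescribed capsules and not 80%, a gap of 8 capsules. Reading the figure as dosing days explains the numbers but gives a rule equivalent to anything from 25 to 30 capsules (71% to 86%).

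The effect is confined to membership of the per-protocol set and to adherence reporting. The SAP gives no adherence data, so neither the number of participants near these cuts nor the size or direction of any effect on the per-protocol estimate can be determined. The arithmetic assumes that Section 7 describes the regimen correctly and, for the days rule, that a day counts only when all its capsules were taken. This should be fixed, but it does not threaten the primary result.

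**What to change.** Reconcile Sections 7, 13 and 19, and state one counting unit that the D14 and D28 logbooks actually record. The worked figure in Sections 13 and 19 should then follow from that unit:
- if capsules, under the Section 7 regimen: 28 of 35;
- if dosing days: 20 of 25, with the word days in place of pills and a statement of what makes a two-capsule day complete.

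If the reconciliation shows that Section 7 misdescribes the regimen, recompute the denominator from the corrected text. No change to the regimen or to the 80% threshold is proposed. Section 15 should point to the single definition.

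Make the change before unblinding and log it in the Section 5 revision table. The SAP's introduction provides that the principal investigator and the trial committees "will be kept blind to the randomization group until final disclosure of the study results", so the correction can be made without knowledge of the groups. If the per-protocol analysis has already been run, document the rule that was used.

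The cost is a wording and number correction in two sections and one cross-reference. No new data are needed, provided that the logbooks record the chosen unit, which the SAP does not show. The per-protocol set may turn out somewhat smaller than under a literal 20-pill cut.

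### The SAP does not settle whether the primary D90 comparison is weighted for dropout, and its extreme-case check, read plainly, does not bound the possible bias

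*SAP*

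**What the plan says.** Five sections of the SAP bear on how participants lost by D90 are handled.

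- **Section 15** counts everyone randomized, including those lost, in the intention-to-treat population.
- **Section 18** opens with "For the primary analyses, we will follow an intention to treat model" and continues, without condition, "We will use an inverse probability of censoring for missing outcome data. Participants lost to follow-up will be censored".
- **Section 23** is the whole of the primary analysis: "The proportions of participants with LONG-COV at D90 will be compared using the Cochran-Mantel-Haenszel test, adjusting for stratification". It mentions no weights, weight covariates, variance method or denominator.
- **Section 17** places weighting elsewhere: "A sensitivity analysis on loss to follow-ups will be performed using weights or extreme case scenarios". Its extreme cases are defined as follows: "we will assume that all losses to follow-up had or did not have LONG-COV at D90, enabling us to estimate the potential bias". It also plans a comparison of follow-up by arm ("Participation in follow-up assessments and completeness of outcome data will be calculated and compared for each time point by study arm") but attaches no decision criterion to it.
- **Section 24** holds the only description of a weighting procedure, for a supplementary secondary model: "If there are differences in censoring by group, an additional GEE model will be used with inverse probability of censoring weights (IPCW"). The method is given in one sentence: "This method first estimates the probability of dropout to construct IPCWs, and then fits the GEE model with these IPCWs".

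**The concern.** Section 18 treats weighting as part of the primary analysis. Section 17 treats it as a possible sensitivity analysis. Section 24 treats it as a conditional add-on to a secondary model. Section 23, where the choice should be fixed, does not mention it. An analyst working from Section 23 alone would run an unweighted CMH on those with D90 data. One working from Section 18 would weight, but would have to choose the covariates and the variance. With more than a fifth of participants lost, the primary p-value should not depend on which section the analyst starts from.

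The backup check is also weak for its stated purpose of estimating the potential bias. If all losses in both arms receive the same value, the result shows how dilution moves the difference. It does not show what happens if lost participants fared differently in the two arms.

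**Working it through.** **1. The plan's own figures.** Section 11 assumes 50% versus 37.5%, two-sided alpha 5% and power 80%. With pooled variance under the null:

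n = [1.960 × √(2 × 0.4375 × 0.5625) + 0.842 × √(0.25 + 0.234375)]² / 0.125² = 246.1, so 247 per arm and 494 in all. 494 / 0.8 = 617.5, so 618. Both reproduce. The point concerns the analysis rule and leaves the sample size unchanged.

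**2. Losses by D90 (Section 16).** The intervention arm has 307 participants: 240 with at least partial D90 data (78.2%) and 67 lost (21.8%). The other arm's denominator is unreadable. 239 + 72 = 311 gives 76.8% and 23.2%, as printed; 310 gives 77.1% and 23.2%, and 312 gives 76.6% and 23.1%. Also 311 + 307 = 618. Total lost: 72 + 67 = 139, and 139/618 = 22.5%. The arms differ by 1.3 points (p = 0.69), so the Section 24 condition, which has no criterion, would probably not be met.

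**3. Why the form of weighting has to be stated.** The ordinary CMH variance treats the cell totals as counts of people. Unscaled inverse-probability weights restore the totals from 479 to about 618, so the statistic is inflated by roughly 618/479 = 1.29. The effective critical value falls to 1.960/√1.29 = 1.73, for a two-sided error of about 8.4%.

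Two illustrative null simulations agree. Each used 618 participants, 8 strata, dropout depending on one assumed binary baseline factor in the same way in both arms, a 30-point risk gap and 4,000 runs.

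| Dropout by factor level | Unweighted CMH | Unscaled weights | Weights scaled to mean 1 |
|---|---|---|---|
| 12.5% / 32.5% | 5.0% | 8.8% | 5.4% |
| 15% / 30% | 5.4% | 8.3% | 5.2% |

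**4. What the extreme cases can show.** Assume the planning rates hold among completers and all 239 + 240 = 479 are evaluable: 119.5/239 (50%) versus 90/240 (37.5%), a difference of 12.5 points (p = 0.006). Differences are placebo minus intervention; p-values are from the unstratified pooled two-proportion test.

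| Assumption for losses | Placebo | Intervention | Difference |
|---|---|---|---|
| All had LONG-COV | 191.5/311 | 157/307 | +10.4 (p = 0.009) |
| None had it | 119.5/311 | 90/307 | +9.1 (p = 0.017) |
| Placebo none, intervention all | 119.5/311 | 157/307 | -12.7 |
| Placebo all, intervention none | 191.5/311 | 90/307 | +32.3 |

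The planned pair is the first two rows.

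A less extreme departure already matters. Let half the placebo losses have LONG-COV: (119.5 + 36)/311 = 50.0%. If 59% of intervention losses have it, (90 + 67 × 0.59)/307 = 42.2%, a difference of 7.8 points with p = 0.052. At 58%, p = 0.045. In this example the planned pair stays significant throughout and does not show that tipping point.

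**The case against.** **Sections 18 and 23 can be read together.** One says how missing outcomes are handled and the other names the test, which gives a weighted stratified comparison. On that reading an unweighted CMH on completers would breach Sections 15 and 18, and the gap is one of detail. This is the best reading, and the fix adopts it. It does not remove the problem: Section 17 lists weights as a sensitivity method, no section gives the primary weight model, and a plausible implementation does not hold 5%.

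**Stronger readings that the SAP does not support.**

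- A reader might infer that a CMH test cannot be weighted. Weighted versions exist; Section 23 simply names none.
- A reader might infer that Section 17 makes the Section 18 weights optional. Its alternative is between two sensitivity methods.
- A reader might infer that the unweighted result would be seriously biased. That needs dropout tied to prognosis differently by arm. In simulations with a true 12.5-point effect and the same dropout pattern in both arms, weighted and completers' analyses disagreed on significance in only 2.8% to 4.0% of trials. Much larger figures arise only if opposite patterns by arm are assumed. Nothing in the SAP points to such patterns: allocation is blinded, the product is described as having few side effects, and losses are nearly equal. Balanced totals do not rule them out either.

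**On the extreme cases.** Arm-specific cases are not excluded by the wording, but none is specified. The planned pair is also not always uninformative. With 96/240 (40%) in the intervention arm, an observed 10.0 points (p = 0.028) falls to 7.2 points (p = 0.062) when no loss has LONG-COV. The opposite extremes are very wide, so a tipping-point grid may be more useful.

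**On the counts.** Section 16 counts participants with at least partial data, and most Section 20 criteria need both D30 and D90. The number with an evaluable primary outcome may therefore be below 479.

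**Conclusion.** The point holds as an inconsistency in the text. Section 18 weights the primary analysis, Section 23 does not say how, and Sections 17 and 24 place weighting in sensitivity and supplementary roles. This part rests on no assumed data. It matters numerically because unscaled weights in the ordinary formula give roughly 8% to 9% type I error in the illustrative settings, against about 5% with weights scaled to mean 1.

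The extreme-case point holds on the plain reading. The planned pair gives 10.4 and 9.1 points, against a range of -12.7 to +32.3. These figures assume planning rates among completers, 311 in the placebo arm and 479 evaluable. They describe the reach of the check and do not predict the result. The Section 24 condition is a lesser matter, since it governs only a supplementary secondary model.

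**What to change.** **Section 23.** Name one primary analysis: a stratified comparison weighted by inverse probability of censoring. Prespecify the weight covariates, for example arm, gender and age strata, baseline severity and earlier-visit symptoms, and use a robust or bootstrap variance. Keep the unweighted CMH on completers as a sensitivity analysis.

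**Section 17.** Align the wording on weights with Section 18. Add the two opposite-arm extreme cases or a tipping-point grid.

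**Section 24 (optional).** Run the weighted GEE whether or not losses are balanced.

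**Section 5.** Log the change as made before unblinding. This matters because the SAP already shows D90 follow-up counts.

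The cost is a few sentences, modest programming and a slightly wider confidence interval.
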